9.0 STUDY CALENDAR

9.1 Arm 1 Hormonal therapy alone

REQUIRED STUDIES	PRE	Mo	Ω						
	STUDY	1	4	7	10	13	16	19	22
PHYSICAL									
History and Physical Exam	X		X	X	X	X	X	X	X
Weight and Performance Status	X		X	X	X	X	X	X	X
Toxicity Notation		X	X	X	X	X	X	X	X
LABORATORY / TESTS									
PSA ¥	X		X	X	X	X	X	X	X
CBC/diff/platelets	X**								
Bilirubin	X**								
SGOT	X**								
Testosterone §	X			X		X		X	
Blood specimens π	X			X					
Tissue Specimen ™	X								
X-RAYS AND SCANS									
Bone Scan §	X								
CT/MRI abdomen and pelvis Σ	X								
OTHER X-RAYS/SCANS									
EKG	X								
MUGA or 2-d Echo	X*								
TREATMENT (Sect. 7.0)									
Radical Prostatectomy ∞	X								
Goserelin acetate (Zoladex®) #		X	X	X	X	X	X	X	X
Bicalutamide (Casodex®) √		X	X	X	X	X	X	X	X

NOTE: All forms to be used for this study are found in Section 18.0. Form submission guidelines are found in Section 14.0.

** Results of these tests do not determine eligibility but should be done prior to registration in accordance with good medical practice (see Section 7.1a). With the exception of blood counts, significant deviations in the values of these tests should be discussed with the Study Coordinator.

These tests are required during treatment as scheduled to assess toxicity.

π Blood specimens for patients opting to participate in the blood and tissue banking should be collected prestudy, between Weeks 24 and 28, and at progression (see Section 15.0).

Σ See Section 5.9. CT scan of abdomen and pelvis must be performed if patient has symptoms of distant metastatic disease.

Every 3 months.

√ Daily.

Ω Treatment and parameters will continue for a total of two years according to the schedule outlined above.

After off treatment, patients will be followed for disease status with Physical Exam and DRE (if PSA \geq 0.1 ng/ml), repeated at end of treatment and every six months for two years and annually thereafter for three additional years. All patients will be followed for 15 years or until death, and PSA will be collected as noted below.

* At prestudy, only for patients with underlying cardiac disease or CHF.

§ For patients with PSA \geq 20 ng/ml at diagnosis.

∞ Must be done within 120 days prior to registration.

™ For patients with adequate tissue and who consent to tissue banking (see Section 15.0 for details).

¥ Testosterone is collected every six months until it reaches the institutional lower limit of normal (ILLN).

PSA is collected every three months for five years, and then every 6 months until 15 years or death.

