1.0 OBJECTIVES

- 1.1 The primary objective is to evaluate overall survival using adjuvant systemic therapy in high risk localized prostate cancer patients following radical prostatectomy. Disease-free survival will also be evaluated. Patients will be randomized to one of the following arms:
 - a. bicalutamide (Casodex[®]) + goserelin acetate (Zoladex[®])
 - b. mitoxantrone + prednisone administered with Casodex[®] + Zoladex[®].
- 1.2 To compare qualitative and quantitative toxicity between the two study arms.
- 1.3 To compare the two treatment arms with respect to PSA progression-free survival.
- 1.4 To test whether PSA progression is a surrogate endpoint for survival or disease-free survival in this clinical trial.
- 1.5 To evaluate promising biomarkers with respect to predicting PSA progression, disease-free survival, and overall survival.
- 1.6 To collect specimens (blood and prostatectomy blocks) for future biomarker (immunohistochemistry, proteomics, genomics) studies and correlations with outcomes.

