Casodex® has been given to over 3,500 men in 35 different clinical studies worldwide, in doses up to 600 mg daily. When Casodex® is given in combination with an LHRH analog, the pharmacologic adverse event profile is dominated by the LHRH analog and includes hot flashes (53%), gynecomastia (9%) and breast pain (6%). Other adverse events reported regardless of causality included diarrhea (12%), constipation (22%), nausea (15%) and abdominal pain (11%). Other adverse were reported, such as fatigue (22%), pain (35%), back pain (25%), pelvic pain (21%), infection (18%), peripheral edema (13%), dyspnea (13%), nocturia (12%), hematuria (12%), anemia (11%), dizziness (10%). Casodex® has been associated with changes in liver function, although these are infrequent (7%) and rarely occur with jaundice. Many of these changes improved or resolved despite continuation of bicalutamide therapy. There have been no reports of fatal hepatotoxicity associated with Casodex® therapy.

c. PHARMACOLOGY

Pharmacokinetics:

Animal studies: After oral single dose administration, absorption of the compound was slow with peak concentration occurring 3 - 12 hours and plateau between 2 and 48 hours. There was non-proportional increase in plasma levels with increasing doses. Elimination half life ranges from 17 - 28 hours in male rats, 21 - 29 hours in female rats and 5 - 7.5 days in dogs. 91 - 96% of Casodex® is bound to plasma protein.

Human studies: After single doses, mean time for peak plasma concentration was 6 hours at 10 and 30 mg, but at 50 mg, it was 16 hours. Mean plasma elimination half lives after 12 weeks of 10, 30, 50, 100 mg/day was 7 - 10 days. This finding was consistent with single dose data. In patients given daily doses of 50 mg, mean plasma concentration was 10 ug/ml at 12 weeks. After single doses, there was linear increase with doses between 10 and 50 mg, but became non-linear at doses of 50 - 100 mg. At 100 mg, the oral bioavailability is reduced by 30% but plasma elimination half life is unchanged. Casodex® is extensively metabolized and metabolites are excreted by both the biliary and urinary system.

Formulation: Casodex® is prepared as round, film-coated green or white tablets containing standard recipients and 50 mg of the drug.

Storage and stability: All packages of Casodex® should be stored securely in a dry place at room temperature.

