8.0 TOXICITIES TO BE MONITORED AND DOSAGE MODIFICATIONS

- 8.1 Patients will be evaluated and graded for toxicity every visit as specified on the Study Calendar for subjective/objective evidence of developing toxicities according to the NCI Common Toxicity Criteria version 2.X (see Section 19.1).
- 8.2 Arm 1 – Hormone therapy
- a. There are no dosage adjustments for hematologic toxicity.
 - b. The most common side effects of anti-androgen therapy are breast pain and gynecomastia. No dose modification is needed except in very severe cases (Grade 3 or higher). In such cases, the anti-androgen will be discontinued permanently and LHRH agonist therapy continued.
 - c. Antiandrogens may be omitted in the case of hepatic toxicity of any severity (at the discretion of the treating physician).
 - d. Hot flashes may develop in patients treated with LHRH agonists. In general, these will not require therapy as resolution is expected following completion of protocol treatment (termination of therapy).
- 8.3 Arm 2 – Mitoxantrone and prednisone + hormone therapy (follow guidelines in Section 8.2 for toxicities attributable to hormone therapy). If mitoxantrone is delayed due to toxicity, prednisone is given on schedule without dose reduction.

- a. Myelosuppression:

See table below for a summary of dose modifications for myelosuppression.

Grade 1, 2 and 3 myelosuppression (leukopenia, neutropenia, thrombocytopenia) and Grade 4 leukopenia or Grade 4 neutropenia except as defined below, with recovery within twenty-one days, does not require dose modification. Patients who do not recover WBC or platelet counts to ≤ CTC Grade 1 toxicity within 21 days should be reduced to dose level -1 for all subsequent courses.

In order to maximize dose intensity, patients with afebrile Grade 4 neutropenia ≥ 7 days or Grade 3 or 4 neutropenia associated with fever (one reading of oral temperature > 38.5°C, or three readings of oral temperature > 38.0°C in a 24-hour period) should be retreated after recovery at the dose level -1.

Grade 4 thrombocytopenia (platelet count < 25,000) at any time necessitates retreatment after recovery at the dose level -1.

G-CSF is not permitted.

Dose Modifications for Myelosuppression.

Dose Level	Mitoxantrone Dose (mg/m ²)
Starting Level	12
Level -1*	9

*This is a permanent dose reduction. Further dose reduction requires removing patient from protocol treatment.

b. Gastrointestinal

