- 11.5 In addition to the study monitoring mentioned above, three formal interim analyses will be done. The decision to terminate accrual early will be made by the DSMC, and will consider disease-free survival, toxicities, and other factors in addition to survival. Additionally, the Southwest Oncology Group Statistical Center will closely monitor throughout the trial whether there is differential use of optional radiotherapy between the two treatment groups and this information will be provided to the DSMC at regular intervals.
- 11.6 The first formal interim analysis will be done after 700 patients have been entered, approximately 6 years after the study opens. Evidence suggesting early termination of the trial would be if the alternative hypothesis of a 30% improvement in survival with the MP + CZ combination arm is rejected at the 0.005 level, using an extension of the logrank test that allows for testing a relative risk not equal to 1. In addition, the null hypothesis of no difference in survival will be tested at the one-sided level of 0.005. The second interim analysis will be performed after 50% of the total expected deaths (275 deaths) will have occurred. Testing will be done as above at the 0.005 level. A third interim analysis will be performed 2.5 years after accrual has been completed. This testing will also be done at the alpha=0.005 level. The final analysis will be performed at the 0.045 significance level, approximately 4 years after accrual has been completed.
- 11.7 Secondary analyses will also be done regarding disease-free survival and toxicities. With 680 patients per arm, toxicity rates can be estimated to within at \pm 4% (95% confidence interval).

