GI30	Constipation/bowel obstruction			SK11	Rash/desquamation		
GI60	Stomatitis/pharyngitis			SK90	Alopecia		
GU00	Incontinence			SX00	Libido loss		
GU03	Urinary frequency/urgency			SX60	Erectile impotence		
HE00	Leukopenia			Other Toxicities (specify):			
HE30	Neutropenia/granulocytopenia			<hr/> <hr/> <hr/>			
ME31	Hyperglycemia			<hr/> <hr/> <hr/>			
MS00	Muscle weakness (not neuro)			<hr/> <hr/> <hr/>			

* Treatment Relation codes: 1-unrelated

2-unlikely

3-possible

4-probable

5-definite

Comments: (Please explain any "other" adverse events reported above, e.g., PA99 Pain-other)

3/15/2006

27242

SOUTHWEST ONCOLOGY GROUP

FOLLOW UP FORM

Page 1 of 1

SWOG Patient ID

SWOG Study No. S

Registration Step

Patient Initials _____ (L, F M)

Institution / Affiliate _____ Physician _____

Participating Group: Group Name/Study No./Patient ID _____ / _____ / _____

Instructions: Please submit at each follow up after completion of treatment until relapse or progression, at time of relapse or progression, and at protocol-specified intervals after relapse or progression. Also submit at time of diagnosis of second primary. All dates are MONTH, DAY, YEAR. Answer all questions and explain any blank fields or blank dates in the **Comments** section. Place an **X** in appropriate boxes. Circle AMENDED items in red.

VITAL STATUS

Vital Status: Alive Dead Date of last contact or death: / /

If vital status is Dead, complete and submit Notice of Death form.

DISEASE FOLLOW UP STATUS

Has the patient had a documented clinical assessment for this cancer (since submission of the previous follow-up form)?

No Yes If Yes, Date of Last Clinical Assessment: / /

NOTICE OF FIRST RELAPSE OR PROGRESSION

Has the patient developed a first relapse or progression that has not been previously reported?

No Yes If Yes, Date of Relapse or Progression: / /

Site(s) of Relapse or Progression: _____

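### On-treatment blood counts, liver tests and LVEF are scheduled only on Arm 2, so between-arm differences in these toxicities will mix drug and testing effects

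*Combined protocol and SAP*

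**What the plan says.** **Objective and analysis.** Objective 1.2 is "To compare qualitative and quantitative toxicity between the two study arms". Section 11.7 adds "Secondary analyses will also be done regarding disease-free survival and toxicities", followed by a precision statement: "With 680 patients per arm, toxicity rates can be estimated to within at" plus or minus "4% (95% confidence interval". Neither section says how unequal testing will be handled. Section 11.5 lists toxicities among the things the DSMC weighs.

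**Arm 1 schedule (9.1).** CBC, bilirubin and SGOT each carry one mark, at prestudy. MUGA or echo is also prestudy only, for patients with underlying cardiac disease or CHF. The footnote to the blood tests nevertheless states "These tests are required during treatment as scheduled to assess toxicity".

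**Arm 2 schedule (9.2).** The same three blood tests are marked repeatedly on treatment, and LVEF has two repeat marks. The fast fact sheet ties the weekly CBC to chemotherapy. A 9.2 footnote limits repeat LVEF to patients who needed one at baseline, whereas Section 8.3c calls for it every second course in every patient.

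**Recording.** Both arms use the Adverse Event Summary Form (Form #27242), which asks for the worst grade in each reporting period. It has pre-printed lines for leukopenia and "Neutropenia/granulocytopenia", but none for anemia, platelets, bilirubin, SGOT or LVEF. Under Sections 14.7 and 14.8 both arms submit it every three months, and Arm 2 also submits it after cycles 3 and 6.

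**Known drug effects.** Section 3.1b reports that bicalutamide, given on both arms, is associated with "changes in liver function, although these are infrequent (7%) and rarely occur with jaundice". It also lists anemia at 11% for bicalutamide with an LHRH analog, regardless of causality. Section 3.3b names myelosuppression and cardiotoxicity as dose-limiting for mitoxantrone and lists mild SGOT elevations as occasional.

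**The concern.** A laboratory abnormality without symptoms is recorded only if someone draws blood. On Arm 2 the calendar ensures that this happens repeatedly; on Arm 1 it depends on an unscheduled test. A between-arm comparison of laboratory toxicity would therefore count Arm 2 more completely than Arm 1.

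Liver changes are the clearest case. Both arms receive bicalutamide, and Section 3.1b says the changes rarely come with jaundice, so most would go unseen without a test. A low Arm 1 rate could be read as absence of toxicity when it partly reflects absence of testing. The excess toxicity attributed to chemotherapy, which is a stated objective and part of what the DSMC sees, would then be too large by an unknown amount.

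**Working it through.** **1. The plan's own figure.** The 95% half-width for a single-arm rate, at the worst case p = 0.5 and n = 680, is 1.96 × √(0.25/680) = 3.76 points. This rounds to the stated 4%. It covers sampling error in one arm's rate and says nothing about whether events were looked for equally.

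**2. Testing artefact when true rates are equal.** Artefact = true rate × (detection on Arm 2 − detection on Arm 1).

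Inputs from the protocol are 7% for liver changes and 11% for anemia (Section 3.1b). Assumptions are the detection fractions, equal true rates, and 488 patients per arm. The permanent-closure memorandum gives 488 for the chemotherapy arm only; the same number is assumed for Arm 1. The z values use the unpooled standard error √[(p₁(1−p₁) + p₂(1−p₂))/488].

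| Event | Detection, Arm 2 / Arm 1 | Recorded, Arm 2 vs Arm 1 | Artefact (points) | z |
|---|---|---|---|---|
| Liver | 100% / 10% | 7.0% vs 0.7% | 6.3 | 5.2 |
| Liver | 100% / 50% | 7.0% vs 3.5% | 3.5 | 2.5 |
| Liver | 50% / 30% | 3.5% vs 2.1% | 1.4 | 1.3 |
| Anemia | 100% / 10% | 11.0% vs 1.1% | 9.9 | 6.6 |
| Anemia | 100% / 50% | 11.0% vs 5.5% | 5.5 | 3.1 |
| Anemia | 50% / 30% | 5.5% vs 3.3% | 2.2 | 1.7 |

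The 50%/30% rows matter because full Arm 2 detection is an upper bound. Six 21-day cycles last 6 × 21 = 126 days, or 18 weeks of a two-year treatment period. The column alignment of the 9.2 table is lost in the text I worked from, so I cannot confirm how far blood testing continues after chemotherapy. At the planned 680 per arm every z is larger by √(680/488) = 1.18, which takes the 50%/30% values to about 1.6 and 2.0.

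**3. When the drug has a real effect.** Suppose true neutropenia rates of 40% on Arm 2 and 5% on Arm 1, full Arm 2 detection and 20-50% Arm 1 detection (all assumed). The true difference is 35 points. The observed difference is 40 − 5 × 0.2 = 39 points, or 40 − 5 × 0.5 = 37.5 points. Testing supplies only 2.5-4 points; the rest is drug effect.

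**The case against.** Four points on the other side stand, and they limit the claim.

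- **Drug effect.** A reader might infer that laboratory differences would be created by testing rather than by drug. The documents do not support that. Section 3.3b expects real myelosuppression and cardiotoxicity, and step 3 shows that a neutropenia difference could be almost entirely real. Even the liver comparison may contain some mitoxantrone effect.
- **No formal test is specified.** Section 11.7 gives per-arm precision only. Objective 1.2 commits to a quantitative comparison but names no test, so the z values show what a naive comparison might produce, not what the plan prescribes.
- **Arm 1 is not blind to laboratory events.** A reader might infer that Arm 1 rates will be zero. The form asks for every observed event, so unscheduled findings can be recorded. Arm 1 detection is likely to be low, but not necessarily nil.
- **Size depends on assumed detection.** With 50% against 30% detection at 488 per arm, neither example reaches 1.96.

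It can also be said that the 9.1 footnote is wording shared with the 9.2 calendar. That may explain it, but on Arm 1 it refers to a schedule with no on-treatment entries. A reader might further see a contradiction with Section 8.2c, "Antiandrogens may be omitted in the case of hepatic toxicity of any severity". That rule is left to the treating physician's discretion and does not by itself imply scheduled liver tests.

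Finally, restricting the comparison to clinical toxicities does not make ascertainment fully equal, because Arm 2 is assessed more often during chemotherapy. That has to be stated with the results. None of these points removes the unequal laboratory schedule or supplies a rule for handling it.

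**Conclusion.** The point holds in limited form. After baseline, CBC, bilirubin, SGOT and LVEF are scheduled only on Arm 2, and the plan for comparing toxicity takes no account of this. Differences in these toxicities will mix drug and testing effects, with Arm 1 under-counted, and the plan gives no means of separating them.

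The problem is most serious for liver changes and anemia and least serious for neutropenia. Under full Arm 2 detection and 10-50% Arm 1 detection, the artefact is 3.5-6.3 points (liver) and 5.5-9.9 points (anemia). It falls to 1.4 and 2.2 points at 50% against 30%. These figures are illustrations resting on assumed detection, equal true rates and an assumed Arm 1 size. The direction is better supported than the size.

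For LVEF the extent of the imbalance cannot be stated, because 8.3c and the 9.2 footnote disagree on who is retested. Under either reading Arm 1 has no scheduled repeat.

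**What to change.** 1. In 1.2 and 11.7, state that the between-arm toxicity comparison covers clinically observed toxicities, taken as each patient's worst grade over the whole protocol treatment period. The whole period is preferable to three-month windows because Arm 2 also reports after cycles 3 and 6. State alongside the results that Arm 2 is assessed more often during chemotherapy.
2. Report hematologic, hepatic-laboratory and LVEF events descriptively by arm, without a between-arm test. Show every recorded Arm 1 event, and label those Arm 1 rates as not systematically assessed so that a low or zero rate is not read as absence of toxicity.
3. Reconcile the 9.1 footnote with the empty Arm 1 on-treatment cells, and reconcile 8.3c with the 9.2 footnote on repeat LVEF.

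Items 1 and 2 change analysis and reporting wording only. They need no new test or visit and can be adopted after accrual has closed. The cost is that there will be no between-arm p-value for laboratory toxicities, a contrast that could not be interpreted cleanly under the present schedule.

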9.0 STUDY CALENDAR

9.2 Arm 2 Hormonal therapy + mitoxantrone + prednisone

	Cy 1	Cy 2	Cy 3	Cy 4	Cy 5	Cy 6	Ω
REQUIRED STUDIES	PRE	Mo					
STUDY	1	Day	Day	Day	Day	Day	
		15	22	36	43	57	
PHYSICAL							
History and Physical Exam	X		X	X	X	X	X X X X X X X X
Weight and Performance Status	X		X	X	X	X	X X X X X X X X
Toxicity Notation	X	X	X	X	X X	X X X	X X X X
LABORATORY / TESTS							
PSA \ddagger	X				X	X X	X X X X X X
CBC/diff/platelets	X**	X X X X X X X X	X X X X X X X X				
Bilirubin	X**	X X X X X X X X	X X X X X X X X				
SGOT	X**	X X X X X X X X	X X X X X X X X				
Testosterone \ddagger	X					X	X X
Blood specimens π	X					X	
Tissue Specimen $^{\text{TM}}$	X						
X-RAYS AND SCANS							
Bone Scan \S	X						
CT/MRI abdomen and pelvis Σ	X						
OTHER X-RAYS/SCANS							
EKG	X						
MUGA or 2-d Echo	X*		X*		X*		
TREATMENT (Sect. 7.0)							
Radical Prostatectomy ∞	X						
Mitoxantrone \P	X	X	X	X	X	X	
Prednisone f	X	X	X	X	X	X	
Goserelin acetate (Zoladex®) #	X				X	X X X X X X X X	
Bicalutamide (Casodex®) ∇	X X X X X X X X	X X X X X X X X	X X X X X X X X	X X X X X X X X			

NOTE: All forms to be used for this study are found in Section 18.0. Form submission guidelines are found in Section 14.0.

** Results of these tests do not determine eligibility but should be done prior to registration in accordance with good medical practice (see Section 7.1a). With the exception of blood counts, significant deviations in the values of these tests should be discussed with the Study Coordinator. These tests are required during treatment as scheduled to assess toxicity.

π Blood specimens for patients opting to participate in the blood and tissue banking should be collected prestudy, between Weeks 24 and 28, and at progression (see Section 15.0).

Σ See Section 5.9. CT scan of abdomen and pelvis must be performed if patient has symptoms of distant metastatic disease.

\P Mitoxantrone will be given on Day 1, every twenty-one days for six cycles.

f Prednisone will be given twice a day continuously for 6 twenty-one day cycles. At the end of prednisone treatment (21 days after last mitoxantrone dose), prednisone should be tapered over 2 - 3 weeks at the discretion of the treating physician.

Every 3 months.

\checkmark Daily.

Ω Treatment and parameters will continue for a total of two years according to the schedule outlined above.

After off treatment, patients will be followed for disease status with Physical Exam and DRE (if PSA \geq 0.1 ng/ml), repeated at end of treatment and every six months for two years and annually thereafter for three additional years. All patients will be followed for 15 years or until death, and PSA will be collected as noted below.

* At prestudy, only for patients with underlying cardiac disease or CHF. Follow-up MUGA or 2-d echo is only needed for those patients who required one at baseline.

\ddagger For patients with PSA \geq 20 ng/ml at diagnosis.

∞ Must be done within 120 days prior to registration.

$^{\text{TM}}$ For patients with adequate tissue and who consent to tissue banking (see Section 15.0 for details).

\ddagger Testosterone is collected every six months until it reaches the institutional lower limit of normal (ILLN).

PSA is collected every three months for five years, and then every 6 months until 15 years or death.

